14.2.3 Follow-up evaluation of target and non-target lesions

To assess tumor response, the sum of diameters for all target lesions is calculated (at baseline and throughout the study). The diameters of any new measurable lesions are included in the sum of diameters at each assessment to provide the total tumor burden. At each assessment, percent change in the sum of diameters is calculated and compared to baseline or to nadir in order to evaluate the target lesion response (including new measurable lesions) (Section 14.2.4). This evaluation combined with the status of non-target lesions (baseline and new non-measurable lesions) is then used to determinate the overall lesion response (Table 14-6). The thresholds for irPR and irPD assessment are the same as for RECIST v1.1.

14.2.4 Definitions of response categories and evaluation of overall lesion response

In irRC, the overall response is primarily based on target lesions (baseline and new measurable lesions). The non-target lesions only contribute to define irCR, and irPD in the case of unequivocal progression, as shown below in [Table 14-6](#).

Like in RECIST 1.1, irCR and irPR must be confirmed at a new assessment after at least 4 weeks. Unlike RECIST 1.1, irPD also requires confirmation at a new assessment after at least 4 weeks.

The response categories are defined as follows:

- Immune related Complete Response (irCR): Disappearance of all non-nodal target lesions and non-target lesions in two consecutive observations not less than 4 weeks apart. In addition, any pathological lymph nodes assigned as target lesions must have a reduction in short axis to < 10 mm. (Sum of diameters may be greater than zero at the time of CR, if nodal lesions are included as target lesions).
- Immune related Partial Response (irPR): At least a 30% decrease in the sum of diameters of all target lesions including new target lesions in two consecutive observations not less than 4 weeks apart, taking as reference the baseline sum of diameters.
- Immune related Progressive Disease (irPD): At least a 20% increase in the sum of diameters of all measured target lesions including new measurable lesions. The irPD must be confirmed in a second evaluation not less than 4 weeks later, taking as reference the smallest sum of diameter of all target lesions recorded at or after baseline (nadir). In addition to the relative increase of 20%, the sum must also demonstrate an absolute increase of at least 5 mm. Worsening of non-target lesions (existing or new) only indicate PD when there is unequivocal evidence of progression, confirmed in a second evaluation not less than 4 weeks later.
- Immune related Stable Disease (irSD): Neither a sufficient shrinkage to qualify for irPR or irCR, nor an increase in lesions which would qualify for irPD.
- Unknown (UNK): Progression has not been documented and one or more target lesions have not been assessed or have been assessed using a method significantly different from baseline that prevents reasonable comparison to the prior assessments.

Table 14-6 Overall response at each assessment

Target and new measurable lesions (Tumor burden), * (%)	Non-target lesions (both baseline and new non-measurable)	Overall lesion response
- 100	Absent	irCR ^a
- 100	Stable/not evaluated	irPR ^a
≤-30 ^b	Absent/Stable/not evaluated	irPR ^a
>-30 ^b and <+20 ^c	Absent/Stable/not evaluated	irSD
≥+20 ^c	Any	irPD ^a
Any	Unequivocal progression	irPD ^a

Target and new measurable lesions (Tumor burden), * (%)	Non-target lesions (both baseline and new non-measurable)	Overall lesion response
* the longest diameter of new measurable lesions is included in the calculation of the sum of longest diameters.		
^a To be confirmed after at least 4 weeks.		
^b From baseline		
^c From nadir		

If the evaluation of any of the target lesions could not be made during follow-up, the overall status must be ‘unknown’ unless progression was documented.

If the evaluation of any non-target lesions is not made, and all target lesions disappeared, irCR cannot be determined and overall response must be “irPR”.

In some circumstances it may be difficult to distinguish residual disease from normal tissue. When the evaluation of complete response depends on this determination, it is recommended that the residual lesion be investigated (fine needle aspirate/biopsy) to confirm the irCR.

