14.1.2.1 Definitions

14.1.2.1.1 Disease measurability

In order to evaluate tumors throughout a study, definitions of measurability are required in order to classify lesions appropriately at baseline. In defining measurability, a distinction also needs to be made between nodal lesions (pathological lymph nodes) and non-nodal lesions.

- **Measurable disease** - the presence of at least one measurable nodal or non-nodal lesion. If the measurable disease is restricted to a solitary lesion, its neoplastic nature should be confirmed by cytology/histology.

For patients without measurable disease see [Section 14.1.3.2.8](#)

Measurable lesions (both nodal and non-nodal)

- **Measurable non-nodal** - As a rule of thumb, the minimum size of a measurable non-nodal target lesion at baseline should be no less than double the slice thickness or 10mm whichever is greater - e.g. the minimum non-nodal lesion size for CT/MRI with 5mm cuts will be 10 mm, for 8 mm contiguous cuts the minimum size will be 16 mm.
- **Lytic bone lesions or mixed lytic-blastic lesions with identifiable soft tissue components**, that can be evaluated by CT/MRI, can be considered as measurable lesions, if the soft tissue component meets the definition of measurability.
- **Measurable nodal lesions (i.e. lymph nodes)** - Lymph nodes ≥ 15 mm in short axis can be considered for selection as target lesions. Lymph nodes measuring ≥ 10 mm and < 15 mm are considered non-measurable. Lymph nodes smaller than 10 mm in short axis at baseline, regardless of the slice thickness, are normal and not considered indicative of disease.
- **Cystic lesions:**
 - Lesions that meet the criteria for radiographically defined simple cysts (i.e., spherical structure with a thin, non-irregular, non-nodular and non-enhancing wall, no septations, and low CT density [water-like] content) should not be considered as malignant lesions (neither measurable nor non-measurable) since they are, by definition, simple cysts.
 - ‘Cystic lesions’ thought to represent cystic metastases can be considered as measurable lesions, if they meet the definition of measurability described above. However, if noncystic lesions are present in the same patient, these are preferred for selection as target lesions.

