14.1.2.3 Baseline documentation of target and non-target lesions

For the evaluation of lesions at baseline and throughout the study, the lesions are classified at baseline as either target or non-target lesions:

- **Target lesions:** All measurable lesions (nodal and non-nodal) up to a maximum of five lesions in total (and a maximum of two lesions per organ), representative of all involved

organs should be identified as target lesions and recorded and measured at baseline. Target lesions should be selected on the basis of their size (lesions with the longest diameter) and their suitability for accurate repeated measurements (either by imaging techniques or clinically). Each target lesion must be uniquely and sequentially numbered on the CRF (even if it resides in the same organ).

Minimum target lesion size at baseline

- **Non-nodal target:** Non-nodal target lesions identified by methods for which slice thickness is not applicable (e.g. clinical examination, photography) should be at least 10 mm in longest diameter. See [Section 14.1.2.1.1](#).
- **Nodal target:** See [Section 14.1.2.1.1](#).

A sum of diameters (long axis for non-nodal lesions, short axis for nodal) for all target lesions will be calculated and reported as the baseline sum of diameters (SOD). The baseline sum of diameters will be used as reference by which to characterize the objective tumor response. Each target lesion identified at baseline must be followed at each subsequent evaluation and documented on eCRF.

- **Non-target lesions:** All other lesions are considered non-target lesions, i.e. lesions not fulfilling the criteria for target lesions at baseline. Presence or absence or worsening of non-target lesions should be assessed throughout the study; measurements of these lesions are not required. Multiple non-target lesions involved in the same organ can be assessed as a group and recorded as a single item (i.e. multiple liver metastases). Each non-target lesion identified at baseline must be followed at each subsequent evaluation and documented on eCRF.

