14.2.1 Introduction

The currently used immune-related response criteria (irRC) uses unidimensional measurements to assess tumor response and it is an adaptation of the original irRC published by Wolchok (Wolchok 2009, Nishino 2013).

The purpose of this document is to summarize the irRC guidelines in details focusing on differences in tumor response assessments between irRC and RECIST v1.1.

The primary difference between irRC and RECIST 1.1 is the definition of progressive disease. The definitions of baseline target/non target lesions, number of lesions selected at baseline, the criteria for lesion measurement method of evaluation of response and definition of response are the same for irRC and RECIST 1.1 and are available in the RECIST 1.1 guidelines (Appendix 1).

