14.2.2 New lesions and non-target lesions

In irRC a new lesion does not automatically indicate progressive disease.

New measurable lesions are added to the sum of diameters of the previously existing target lesions, and the sum of diameters is followed at each subsequent tumor assessment.

New measurable lesions are defined using the same criteria as for baseline target lesions in RECIST v1.1. New measurable lesions shall be prioritized according to size, and the largest lesions shall be selected as new measurable lesions. Up to five new measurable (and a maximum of two per organ) are allowed in total and will be included in the overall tumor assessment.

Non-target lesions (baseline and new non-measurable lesions) are used primarily for determination of Complete Response (CR). The RECIST v1.1 definitions for the assessment of non-target lesions apply. A CR requires that all non-target lesions disappear (both those present at baseline and any new non-measurable lesions that have appeared during the study). If after worsening a non-target lesion becomes measurable, it should still be followed as a non-target lesion. Worsening of non-target lesions and new non-measurable lesions only indicate disease progression if there is unequivocal evidence of disease progression (Table 14-6).

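### The Table 14-6 footnote puts new measurable lymph nodes into the irRC sum by longest diameter, against the short-axis rule of Appendix 1, and can change some secondary irRC categories

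*Protocol*

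**What the plan says.** **Appendix 1 (RECIST 1.1).** Section 14.1.2.1.1 sets the entry size for a node by short axis: "Lymph nodes ≥ 15 mm in short axis can be considered for selection as target lesions". Section 14.1.2.3 builds the sum on two axes: "A sum of diameters (long axis for non-nodal lesions, short axis for nodal) for all target lesions will be calculated".

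**Appendix 2 (irRC), general text.** Section 14.2.1 states that "the criteria for lesion measurement method of evaluation of response and definition of response are the same for irRC and RECIST 1.1". Section 14.2.2 adds that "New measurable lesions are defined using the same criteria as for baseline target lesions in RECIST v1.1" and caps their number: "Up to five new measurable (and a maximum of two per organ) are allowed in total". Section 14.2.3 describes the sum without naming an axis: "The diameters of any new measurable lesions are included in the sum of diameters at each assessment".

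**Appendix 2, Table 14-6.** The footnote is the only sentence that names an axis for new lesions in the irRC sum: "the longest diameter of new measurable lesions is included in the calculation of the sum of longest diameters". The first row of the table gives irCR at a change of -100%, whereas the irCR definition in the text of 14.2.4 notes: "Sum of diameters may be greater than zero at the time of CR, if nodal lesions are included as target lesions".

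**SAP.** Section 2.7.2 has the irRC endpoints analysed, and the Bayesian analysis repeated on irRC response, but neither it nor 2.7.3 gives a measurement rule for irRC.

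**The concern.** A new node qualifies for the sum by its short axis but, under the footnote, enters by its long axis. If the existing nodes stay on short axis as Appendix 1 requires, one sum mixes two scales. The long axis is never smaller than the short axis, so when the node first appears the footnote can only raise the total: towards irPD, or away from irPR.

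At stake are the secondary irRC endpoints (ORR, PFS, DOR, DCR, CBR) and the repeated Bayesian analysis. Response is assigned by local investigators (Protocol 7.2.1), so sites could read the rule differently. Confirmed irPD also bears on stopping treatment (Protocol 7.1.2), which is a further reason to have one consistent text.

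**Working it through.** The plan gives no figure on this point to reproduce. The check applies the protocol's own thresholds to the same node measured in two ways.

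**Inputs from the protocol**
- Smallest measurable node: 15 mm short axis (14.1.2.1.1).
- irPD: a rise of at least 20% from nadir and at least 5 mm, confirmed after at least 4 weeks (14.2.4).
- irPR: a fall of at least 30% from baseline (14.2.4).

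**Assumptions**
- One new node, short axis s = 15 mm, long axis l = 24 mm (range 18 to 30 mm).
- Other lesions unchanged at the nadir sum S, which is kept on the Appendix 1 axes.
- No unequivocal progression of non-target lesions.

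**irSD to irPD.** A new node of size x changes the sum by x/S. It reaches +20% when S <= x/0.20. The 5 mm condition is met on either axis. The category therefore differs when s < 0.20 x S <= l, that is, when 5s < S <= 5l.
- Short axis: 15/0.20 = 75 mm.
- Long axis 24 mm: 24/0.20 = 120 mm, so the category differs for S above 75 mm and up to 120 mm.
- Long axis 18 mm: 18/0.20 = 90 mm. Long axis 30 mm: 30/0.20 = 150 mm.

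| Nadir S (mm) | Node (mm) | By short axis | By longest diameter |
|---|---|---|---|
| 60 | 15 x 18 | 15/60 = +25.0%, irPD | 18/60 = +30.0%, irPD |
| 80 | 15 x 18 | 15/80 = +18.8%, irSD | 18/80 = +22.5%, irPD |
| 100 | 15 x 18 | 15/100 = +15.0%, irSD | 18/100 = +18.0%, irSD |
| 100 | 15 x 24 | 15/100 = +15.0%, irSD | 24/100 = +24.0%, irPD |

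Each irPD is unconfirmed at this point. A node that persists at the same size would confirm it on the same measurement.

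**irPR to irSD.** Take a baseline of 100 mm, which is also the nadir so far, with existing lesions at 55 mm at the assessment where the 15 x 24 mm node appears. By short axis the sum is 55 + 15 = 70 mm, or -30%: irPR. By longest diameter it is 55 + 24 = 79 mm, or -21%: irSD.

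**The irCR row.** Take a baseline sum of 60 mm, all non-nodal and non-target disease gone, and a target node now at 8 mm. The change is (8 - 60)/60 = -86.7%. The text of 14.2.4 gives irCR; the table gives irPR. It cannot be worse than irPR: each target node was at least 15 mm at baseline and is below 10 mm at irCR, so with no new lesion in the sum the remaining fraction is below 10/15 = 66.7%. The fall exceeds 33.3% and always passes the 30% threshold. Only the split between irCR and irPR moves; irRC ORR, CBR and DCR do not.

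**The case against.** The strongest reply is that the documents largely settle the axis. Section 14.2.1 adopts the RECIST 1.1 measurement criteria and refers to Appendix 1. Section 14.2.2 ties new measurable lesions to the target-lesion criteria. Section 14.2.3 builds the sum before Table 14-6 is applied. On this view the footnote is loose shorthand. The footnote also calls the total a sum of longest diameters; read literally throughout, existing nodes would be on long axis too and the scales would not be mixed.

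The first part stands as evidence of intent. It does not remove the conflict: no text says which statement prevails, and only the footnote names an axis for new lesions. The second part exchanges one contradiction for another, because the whole sum would then depart from 14.1.2.3. It does show that the ranges above depend on the existing sum being kept on the Appendix 1 axes.

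A reader might infer more than the documents support:
- **That all new lesions are affected.** Only new measurable nodes counted in the sum are, within the cap of five lesions and two per organ. Nodes of 10 mm to under 15 mm short axis do not enter.
- **That the footnote by itself takes patients off treatment.** irPD needs confirmation, and Protocol 7.1.2 allows some patients with confirmed irPD to continue.
- **That the primary results are biased.** Primary ORR and CBR use RECIST v1.1, where a new lesion is progression whatever its axis (14.1.2.4.4).
- **That groups failed to expand because of it.** irRC responses did count towards expansion, but Amendment 05 records that the criteria were not met and enrolment is closed. Nothing shows that a count was affected.

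**Conclusion.** The point holds as an internal contradiction with a limited, conditional effect. Taken literally, the footnote can assign a different irRC category to a patient with a new measurable node. For a 15 x 24 mm node the window for irSD against irPD is a nadir sum above 75 mm and up to 120 mm; the upper limit is 90 to 150 mm for long axes of 18 to 30 mm. These node sizes, and the unchanged other lesions, are assumptions. The 15 mm minimum and the 20% and 5 mm thresholds are the protocol's.

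The share of patients in such a window, and the axis that sites actually used, cannot be learned from the documents. A claim that the irRC results are in fact biased towards progression would go too far. The irCR row is a second, smaller contradiction that changes only how responders divide between irCR and irPR. Both are worth correcting because the secondary irRC endpoints and the repeated Bayesian analysis rest on these categories.

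**What to change.** 1. Reconcile the Table 14-6 footnote with 14.1.2.3 and 14.2.1, so that new measurable lesions enter the sum by long axis if non-nodal and by short axis if nodal.
2. Reconcile the irCR row with the irCR definition in the text of 14.2.4, so that -100% is not required when target nodes remain at normal size.
3. State the same measurement rule in SAP 2.7.2 and derive and report the irRC endpoints on it.
4. Check which axis sites recorded for new nodes. For patients with a new node in the sum, recompute the category on the stated rule and query those that differ from the investigator's.

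Where irPD governs the stopping of treatment, the passages must be reconciled; no clinical rule is proposed here.

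The cost is two wording changes, one SAP sentence and a derivation check. Some new nodes may need re-measuring from existing scans if only long axes were recorded.

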14.2.5 Only non-measurable disease at baseline

For patients with only non-measurable disease at baseline, unequivocal progression of non-target lesions will constitute an irPD (i.e. worsening of the overall tumor burden which is substantial enough to lead to discontinuation or change of therapy). In addition, the appearance of new lesions (measurable or non-measurable) consistent with unequivocal progression taking into account the overall disease burden will constitute an irPD. The absence of all non-target lesions and no new lesions will qualify for irCR. Otherwise the overall response will be considered as irNon-CR/Non-PD (irNCRNPD) similar to RECIST 1.1. Confirmation of irPD and irCR as specified above in Section 14.2.4 is required. If any baseline non-target lesion or a new lesion observed at an earlier post-baseline evaluation was not/could not be assessed at a later post-baseline tumor evaluation then the overall response will be irUNK. No confirmation is required for irNCRNPD.

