5.2 Inclusion criteria

Patients eligible for inclusion in this study have to meet **all** of the following criteria:

1. Written informed consent must be obtained prior to any procedures
2. Age \geq 18 years [For Japan only: written consent is necessary both from the patient and his/her legal representative if he/she is under the age of 20 years.]
3. Phase Ib part: Patients with advanced melanoma, endometrial carcinoma, pancreatic or TNBC, with measurable or non-measurable disease as determined by RECIST v 1.1 (refer to [Appendix 1](#)), who have progressed despite standard therapy or are intolerant of standard therapy, or for whom no standard therapy exists.
4. Phase II part: Patients with advanced solid tumors, with at least one measurable lesion as determined by RECIST version 1.1, who have received standard therapy (no more than 3 prior lines of treatment) or are intolerant of standard therapy, have progressed following their last prior therapy, and fit into one of the following groups:
 - Group 1: TNBC who did not receive prior anti-PD-1/PD-L1 treatment

- Group 2: Pancreatic adenocarcinoma who did not receive prior anti-PD-1/PD-L1 treatment
 - Group 3: Endometrial carcinoma who did not receive prior anti-PD-1/PD-L1 treatment
 - Group 4: Melanoma who progressed on prior anti PD-1/ PD-L1-directed treatment.
5. ECOG performance status ≤ 2
 6. Patient must have a site of disease amenable to biopsy, and be a candidate for tumor biopsy according to the treating institution's guidelines. Patient must be willing to undergo a new tumor biopsy at screening, and during therapy on this study. Patients with an available archival tumor tissue collected less than 6 months before study startup do not need to perform a tumor biopsy at screening.

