14.1.2.4.3 Determination of non-target lesion response

Table 14-2 Response criteria for non-target lesions

Response Criteria	Evaluation of non-target lesions
Complete Response (CR):	Disappearance of all non-target lesions. In addition, all lymph nodes assigned a non-target lesions must be non-pathological in size (< 10 mm short axis)
Progressive Disease (PD):	Unequivocal progression of existing non-target lesions. ¹
Non-CR/Non-PD:	Neither CR nor PD
Unknown (UNK)	Progression has not been documented and one or more non-target lesions have not been assessed or have been assessed using a different method than baseline.

¹. Although a clear progression of non-target lesions only is exceptional, in such circumstances, the opinion of the treating physician does prevail and the progression status should be confirmed later on by the review panel (or study chair).

Notes on non-target lesion response

- The response for non-target lesions is **CR** only if all non-target non-nodal lesions which were evaluated at baseline are now all absent and with all non-target nodal lesions returned to normal size (i.e. < 10 mm). If any of the non-target lesions are still present, or there are any abnormal nodal lesions (i.e. ≥ 10 mm) the response can only be ‘**Non-CR/Non-PD**’ unless any of the lesions was not assessed (in which case response is **UNK**) or there is unequivocal progression of the non-target lesions (in which case response is **PD**).
- **Unequivocal progression:** To achieve “unequivocal progression” on the basis of non-target disease there must be an overall level of substantial worsening in non-target disease

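### Section 14.2.5 gives both irPD and irUNK for the same scan when non-measurable disease has clearly progressed but another lesion was not assessed

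*Protocol*

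**What the plan says.** Section 14.2.5 (Protocol Appendix 2) sets the irRC rules for patients who have only non-measurable disease at baseline. Four of its statements matter here.

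- On existing disease: "unequivocal progression of non-target lesions will constitute an irPD".
- On new disease: "the appearance of new lesions (measurable or non-measurable) consistent with unequivocal progression taking into account the overall disease burden will constitute an irPD".
- On confirmation: "Confirmation of irPD and irCR as specified above in Section 14.2.4 is required".
- On incomplete evaluations, the sentence begins "If any baseline non-target lesion or a new lesion observed at an earlier post-baseline evaluation was not/could not be assessed at a later" evaluation, and its consequence is an overall response of irUNK.

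The first two do not require every lesion to have been assessed. The last has no exception for documented progression.

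The corresponding rules elsewhere do have one. In Table 14-2 (RECIST non-target lesions), the unknown category begins "Progression has not been documented and one or more non-target lesions have not been assessed". Section 14.1.2.5 makes the RECIST overall status unknown for an unevaluated lesion except where progression was seen. In Section 14.2.4, the text below Table 14-6 makes the status unknown for an unevaluated target lesion "unless progression was documented".

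Such patients can be in the trial because Phase Ib admits patients "with measurable or non-measurable disease as determined by RECIST v 1.1". Phase II requires at least one measurable lesion.

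**The concern.** An evaluation can show unequivocal progression at one site while another site was not imaged. Section 14.2.5 then yields irPD from one sentence and irUNK from another, both mandatory, with no order of precedence. The irUNK sentence comes last and sits in the section written for these patients, so an investigator or programmer could reasonably apply it as it stands.

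The endpoint mainly exposed is PFS per irRC in Phase Ib, a secondary endpoint. An evaluation recorded as irUNK is neither a progression event nor a valid assessment of non-progression. Because irPD needs a second evaluation, a gap at either of the two evaluations can matter.

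**Working it through.** No rate or sample size is involved, so the check is a comparison of rules on one case. The patient has only non-measurable disease. At an evaluation, lesion A has unequivocally progressed and lesion B, present at baseline, was not assessed.

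| Rule | Classification |
|---|---|
| Table 14-2 (RECIST, non-target) | PD; unknown is not available once progression is documented |
| Section 14.1.2.5 (RECIST, overall) | PD; the unknown rule yields to progression |
| Section 14.2.2 (irRC) | Applies the RECIST definitions for assessing non-target lesions, so Table 14-2 carries over |
| Table 14-6 (irRC) | irPD, to be confirmed: unequivocal non-target progression with any tumour burden |
| Section 14.2.5, progression sentence | irPD, to be confirmed |
| Section 14.2.5, incomplete-evaluation sentence | irUNK |

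One sentence disagrees with all the others, including one in its own paragraph.

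**Effect if the irUNK sentence is applied literally.** Protocol Section 7.2.1 schedules scans every 2, then 3, then 4 cycles of 21 days: 2 × 3 = 6 weeks, 3 × 3 = 9 weeks, 4 × 3 = 12 weeks.

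1. *Gap only at the first progressing scan.* That scan is irUNK. The first irPD moves to the next scan, 6, 9 or 12 weeks later by schedule.
2. *Gap only at the confirming scan.* The first irPD stands but is unconfirmed. Section 14.2.4 sets a minimum of 4 weeks for confirmation and no maximum, so a later complete scan can still confirm it.
3. *Gap at every later scan,* for example a lesion that can never be assessed again. irPD is never reached. Under SAP Section 2.7.3 a patient without documented progression or death is censored at the last valid assessment showing non-progression.
4. *Progression or death after two or more consecutive irUNK scans.* SAP Section 2.7.3 censors events that follow two or more consecutive missing assessments. Whether irUNK counts as missing is not stated. Protocol Section 14.1.4.5.6 points that way, since it treats a run of only unknown assessments before cut-off as adequate assessment no longer being available. This case therefore rests on an assumption.

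**Who can be affected.** The study status under Amendment 05 gives 60 patients treated in dose escalation and 81 in Phase II. The number of Phase Ib patients with only non-measurable disease is not given, so the range is 0 to 60. By design it is none of the 81. The Phase II primary ORR and CBR are defined by RECIST v1.1 and do not use Section 14.2.5.

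**The case against.** The strongest reply is that Appendix 2, read as a whole, already gives the answer. The same paragraph calls unequivocal progression irPD, Table 14-6 agrees, and Section 14.2.2 brings in the RECIST non-target definitions, under which unknown requires that progression is not documented. On that reading irUNK covers only scans where progression has not been established. Response is also the local investigator's assessment (Protocol Section 7.2.1), and neither document says that the irUNK sentence would be programmed over an investigator's irPD.

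Much of this stands. It shows what was probably intended, and that the text is contradictory rather than a clear rule in favour of irUNK. It does not remove the contradiction. The irRC exceptions in Section 14.2.4 are worded for target lesions, which these patients do not have. Section 14.2.2 imports definitions for assessing non-target lesions, whereas the disputed sentence sets the overall response. Reliance on the investigator also cuts both ways: one who follows the sentence literally would record irUNK, and Protocol Section 14.1.4.4 says the investigator's assessment is not overruled.

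A reader might infer that Section 14.2.5 overrides irPD and removes clear progression from PFS per irRC. The documents do not support that. Nothing gives the irUNK sentence priority, a single irUNK scan does not remove an event, and death remains a PFS event.

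A reader might also take Table 14-4, the RECIST table for patients with non-target disease only, as the model to follow. For new lesions it is not one: it makes any new lesion PD, while Section 14.2.2 says that under irRC a new lesion is not automatically progression.

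Nor is this a live treatment problem in the affected group. At 08-Jul-2019 the 6 patients still on treatment were all in Phase II.

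**Conclusion.** The contradiction is real and minor. For non-measurable disease only, Section 14.2.5 does not settle whether irPD or irUNK applies when progression is unequivocal but another lesion was not assessed. The usual consequence of a literal reading is an irPD that is delayed by a scan interval or left unconfirmed. Censoring in place of an event needs a persistent gap or, where an event follows two or more irUNK scans, the assumption that irUNK counts as missing.

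How often lesions go unassessed is not stated in either document, so the number of altered PFS times cannot be estimated. Only secondary irRC results in Phase Ib are exposed.

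**What to change.** **Analysis.** Add a derivation line to the SAP for patients with only non-measurable disease: irUNK for an unassessed lesion applies only to evaluations where unequivocal progression, of non-target disease or by new lesions consistent with it, is not documented. Where it is documented, the evaluation is irPD, still subject to confirmation. This agrees with Section 14.2.2, Table 14-2 and Table 14-6 and keeps the irRC treatment of new lesions. The same line should say whether irUNK counts as a missing assessment under SAP Section 2.7.3.

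**Treatment decisions.** The two sentences of Section 14.2.5 must be reconciled. This review does not say how.

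**Cost.** One line in the SAP, by amendment before database lock or addendum after it, as SAP Section 1 provides. The matching clause in Appendix 2 can go into any further protocol amendment. It would help to count the Phase Ib patients with only non-measurable disease and list their irUNK evaluations. If there are none, the change has no effect on results.
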